9.2.8. Medication Errors

Medication error refers to any unintended error in the dosing and/or administration of the study treatment as per instructions in the protocol. Medication errors generally fall into 4 categories as follows:

- Wrong study drug/device
- Wrong dose (including dosing regimen, strength, form, concentration, amount)
- Wrong route of administration
- Wrong participant (ie, not administered to the intended participant)

Medication errors include occurrences of overdose and underdose of the study treatment.

Overdose: Unintentional administration of a quantity of the study treatment given per administration or per day that is above the maximum recommended dose (10 µg BID or 20 µg/day) according to the reference safety information or protocol for the study treatment or comparator as applicable. This also takes into account cumulative effects due to overdose.

Underdose: Unintentional administration of a quantity of the study treatment given per administration or per day that is under the minimum recommended dose according to the reference safety information or protocol. Since there is no clinical information on the efficacy of relamorelin at a dose less than 10 µg BID, a dose of 10 µg once daily should be considered an underdose.

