10.3.3. Safety Analyses

All safety analyses will be performed on the Safety Population.

The following safety categories will be summarized as appropriate (eg, categorical or continuous descriptives, shift tables) for the safety population and will be fully defined in the SAP.

- AEs
 - Clinically significant hyperglycemia- and hypoglycemia-related events
- Clinical laboratory assessments
 - Potential Hy's law cases
- Vital signs
- ECGs
- Study-specific assessments
 - HbA1c

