6.4 Safety Population

The Safety Population will consist of all participants in the ITT population who received ≥ 1 administration of study treatment.

The Safety Population will be used for all safety analyses. Participants will be analyzed according to the treatments they are planned during the study.

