6.5 Randomized Withdrawal Population

The Randomized Withdrawal (RW) Population will consist of all participants who are re-randomized or assigned to a treatment of the RW Period and receive ≥ 1 administration of study treatment during the RW Period. For the RW Period, there are 3 treatment sequences as follows:

1. Placebo - 10 μg (Placebo BID in the Treatment Period, followed by Relamorelin 10 μg BID in the RW Period)
2. 10 μg - 10 μg (Relamorelin 10 μg BID in the Treatment Period, followed by Relamorelin 10 μg BID in the RW Period)
3. 10 μg - Placebo (Relamorelin 10 μg BID in the Treatment Period, followed by placebo BID in the RW Period)

For the analyses based on RW Population, participants will be analyzed according to the treatments they are planned in the lead-in studies RLM-MD-01 and RLM-MD-02 and the RW period.

7 Participant Disposition

Screen failures (ie, participants who signed informed consent form, but did not enter the 40-week Treatment Period (ie, participants who were not dispensed study treatment at Visit 1 of this study)) and the associated reasons will be tabulated by treatment group and pooled across treatment group for the Screened Population. The number and percentage of participants who complete the double-blind Treatment Period and of participants who prematurely discontinue during the same period will be presented for each treatment group and pooled across treatment groups for the ITT Population. The reasons for premature discontinuation from the double-blind Treatment Period as recorded on the termination pages of the electronic case report forms will be summarized (number and percentage) by treatment group and pooled across treatment groups. All participants who prematurely discontinue during the double-blind Treatment Period will be listed by discontinuation reason.

Similar to the double-blind Treatment Period, the number and percentage of patients who are re-randomized into the RW Period, complete the RW Period, and prematurely discontinue from the RW Period will be presented overall and by treatment sequence for the RW Population. Reason for premature discontinuation from the RW Period as recorded on the trial completion forms of the eCRFs will be summarized (number and percentage) by treatment sequence.

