The number and percentage with significant protocol deviations in the double-blind Treatment Period and in RW Period will be presented by treatment group and overall and by treatment sequence for the ITT Population and the RW Population, respectively.

8 Demographics and Other Baseline Characteristics

Demographic parameters (eg, age, age group, race, ethnicity, sex, geographic region), using the demographic and baseline data from lead-in studies RLM-MD-01 and RLM-MD-02, will be summarized in total and by treatment group for the Safety Population and RW Population.

Abnormalities in participants' medical and surgical histories will be coded using the *Medical Dictionary for Regulatory Activities*, version 23.1 or newer. A data listing for medical and surgical histories will be presented.

Prior medication is defined as any medication started before the date of the first dose of double-blind study treatment from the lead-in studies RLM-MD-01 and RLM-MD-02. *Concomitant medication* is defined as any medication taken on or after the date of the first dose of double-blind study treatment in this study.

The *WHO Drug Dictionary*, Version B2 March 2017 or newer, will be used to classify prior and concomitant medications by WHO Drug Anatomical/Therapeutic/Chemical (ATC) category and drug preferred name. A data listing for prior and concomitant medications will be presented.

9 **Extent of Exposure**

A listing of the investigational product dosing records will be provided for ITT population.

10 Efficacy Analyses

The efficacy analyses for the double-blind Treatment Period will be based on the mITT Population. For the RW Period, the efficacy analyses will be based on the RW Population. Since the study was early terminated, only descriptive analyses for the primary and secondary efficacy endpoints will be performed.

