10.2 Secondary Efficacy Endpoints

- **Nausea Week 12 responder:** Nausea responder defined as a participant who has a ≥ 2 -point improvement in the weekly symptom score at each of the last 6 weeks of the first 12 weeks of the 40-week Treatment Period
- **Abdominal pain Week 12 responder:** Abdominal pain responder defined as a participant who has a ≥ 2 -point improvement in the weekly symptom score at each of the last 6 weeks of the first 12 weeks of the 40-week Treatment Period
- **Bloating Week 12 responder:** Bloating responder defined as a participant who has a ≥ 2 -point improvement in the weekly symptom score at each of the last 6 weeks of the first 12 weeks of the 40-week Treatment Period

- Postprandial fullness Week 12 responder: Postprandial fullness responder defined as a participant who has a ≥ 2 -point improvement in the weekly symptom score at each of the last 6 weeks of the first 12 weeks of the 40-week Treatment Period
- Change from Baseline to Week 40 in Average Weekly DGSSS: Average weekly scores are derived as the average of the weekly scores from Week 37 to Week 40
- Change from Baseline to Week 46 in Average Weekly DGSSS: Average weekly scores are derived as the average of the weekly scores from the six weeks of the Randomized Withdraw Period
- Change from Baseline to Week 40 in Vomiting Frequency: Average weekly number of vomiting episodes are derived as the average of the weekly number of vomiting episodes from Week 37 to Week 40
- Change from Baseline to Week 46 in Vomiting Frequency: Average weekly number of vomiting episodes are derived as the average of the weekly number of vomiting episodes from the six weeks of the Randomized Withdraw Period
- Vomiting Week 40 Responder: Vomiting responder defined as a participant with zero weekly vomiting episodes during each of the last 4 weeks of the 40-week Treatment Period(Week 37 to Week 40)

11 Safety Analyses

The safety analysis for the double-blind Treatment Period will be performed using the Safety Population. For the RW Period, the safety analysis will be performed using the RW Population. The safety parameters will include adverse events (AEs), clinical laboratory, electrocardiogram, and vital sign parameters.

The Day 1 for the safety analyses in the double-blind treatment period is the date of the first double-blind study treatment in this study. Day 1 for the safety analyses in the RW period is the re-randomization date.

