11.1 Adverse Events

Adverse events will be coded by system organ class and preferred term using the *Medical Dictionary for Regulatory Activities (MedDRA)*, version 23.0 or newer.

An AE will be considered a treatment-emergent adverse event (TEAE) for the study if it was present after the first dose of study intervention or was present before the date of the first dose of study intervention and increased in severity or became serious after the first dose of study treatment during the study. Per case report form instructions, a new AE record will be created with a new AE onset date for any AE that worsens. Therefore, TEAEs can simply be identified as those AEs with recorded onset date on or after the date of the first dose of study intervention and within 30 days of the last dose of study intervention in the study. An AE that occurs more than 30 day after the last dose of study drug in the study will not be counted as a TEAE for the study.

An AE will be considered a treatment-emergent SAE (TESAE) if it is a TEAE that also is an SAE.

All TEAEs related summary will be presented by treatment group for the Treatment Period and by treatment sequence for the RW Period separately. A TEAE will only be counted in the double-blind treatment period if it starts between the date of the first dose of study treatment (inclusive) in the double-blind treatment period and the date of the first dose of study treatment (exclusive) in the RW period or within 30 days of the date of the last dose of study treatment in the double-blind treatment period if the patient did not enter the RW period. A TEAE will only be counted in the RW period if it starts on or after the first dose of study treatment in the RW period and within 30 days of the date of the last dose of study treatment in the RW period.

The number and percent of participants with TEAEs, TEAEs leading to discontinuation from study, Deaths, SAEs and TESAEs will be presented by treatment group for the Treatment Period, and by treatment sequence for the RW Period separately.

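### Safety tables for both periods group participants by planned treatment, so any events on a wrong kit would be credited to a treatment the participant was not taking

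*SAP*

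**What the plan says.** Membership of the safety set depends on exposure. SAP 6.4: "The Safety Population will consist of all participants in the ITT population who received ≥ 1 administration of study treatment". The arm label does not. The same section continues: "Participants will be analyzed according to the treatments they are planned during the study".

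SAP 6.5 also requires at least one dose in the RW Period for entry to the RW Population, and then states that "participants will be analyzed according to the treatments they are planned in the lead-in studies RLM-MD-01 and RLM-MD-02 and the RW period". SAP 11 makes this the RW safety set: "For the RW Period, the safety analysis will be performed using the RW Population".

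These labels define the safety tables. SAP 11.1: "All TEAEs related summary will be presented by treatment group for the Treatment Period and by treatment sequence for the RW Period separately". SAP 11.2 splits the PCS laboratory table the same way.

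The protocol sets no competing rule. Section 10.3.3 says only "All safety analyses will be performed on the Safety Population", and Table 10-1 defines that population without saying how the arm is assigned. Protocol 9.2.8 names "Wrong study drug/device" as one category of medication error. On dosing actually taken, SAP 9 offers a listing: "A listing of the investigational product dosing records will be provided for ITT population".

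**The concern.** Planned grouping suits efficacy because it preserves the randomised comparison. For safety the question is what happened to people while they were exposed to the drug. Here exposure decides who enters the tables, and dose dates decide which events count as treatment-emergent (SAP 11.1), but the treatment heading comes from the plan. A participant assigned placebo who was handed relamorelin would carry any resulting event into the placebo column.

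Mixing treatments between columns generally makes the groups look more alike, which is the unhelpful direction when looking for harm. It matters more here because the study stopped early. SAP 4, 10 and 16 describe an abbreviated report built on selected safety outputs, with efficacy only descriptive, so the safety tables are its main content.

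**Working it through.** The plan states no figure for this rule, and neither document reports wrong-kit cases. The check therefore has two parts: whether anything overrides the rule, and how large the effect could be under stated assumptions.

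**1. Does anything override the rule?**
- Protocol Table 10-1 and 10.3.3: population only, no arm-assignment rule.
- SAP 7: counts of significant protocol deviations by treatment group and by sequence. No event is moved.
- SAP 9: a listing of dosing records. It is not an as-treated table.
- SAP 16: describes the abbreviated scope. It does not mention arm assignment.

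Nothing overrides it, and there is no rule for mixed exposure.

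**2. Whole-period crossover (upper bound).** Let pR and pP be the true event risks on relamorelin and placebo, and let a share m of each planned arm take the other treatment throughout.
- Planned relamorelin arm: (1−m)pR + m·pP
- Planned placebo arm: (1−m)pP + m·pR
- Difference: (1−2m)(pR−pP)

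With assumed risks of 20% and 10% (true difference 10.0 points):

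| m (assumed) | Factor 1−2m | Difference shown |
|---|---|---|
| 0% | 1.00 | 10.0 points |
| 0.5% | 0.99 | 9.9 |
| 1% | 0.98 | 9.8 |
| 2% | 0.96 | 9.6 |
| 3% | 0.94 | 9.4 |
| 5% | 0.90 | 9.0 |

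**3. One wrong pen.** Protocol Table 7-1 gives each pen 28 days of use. The Treatment Period is 40 × 7 = 280 days, so about 280/28 = 10 pens, and one wrong pen is a fraction f = 0.1 of exposure. If risk accrues evenly over time, the factor becomes 1−2mf. At m = 1% it is 1 − 2(0.01)(0.1) = 0.998; at m = 3% it is 0.994. In the RW Period one pen is 28/(6 × 7) = 28/42, or 67% of exposure, so a single error weighs much more there.

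**4. One participant in the RW Period.** Protocol 5.2 expects 600 completers. With equal attrition, 600/2 = 300 had relamorelin in the Treatment Period, and 1:1 re-randomization gives 300/2 = 150 per sequence. One misplaced participant who had the event shifts that sequence's rate by about 1/150 = 0.67 points. If early termination left an assumed 30 per sequence, the shift is 1/30 = 3.3 points. The difference between the two sequences involved can move by up to twice this. Without the event, only the denominator changes. The RW Population also includes people who drop out during the RW Period, so under the planned numbers 150 is somewhat low and 0.67 somewhat high.

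**5. A rare event.** The planned arm size is 2 × 300 × 0.8 = 480 (Protocol 10.1). Assume 4 versus 0 events by treatment received, one of the four in a participant assigned placebo who was on a relamorelin kit. With denominators held at 480:
- By treatment received: 4/480 = 0.83% versus 0%
- By planned treatment: 3/480 = 0.63% versus 1/480 = 0.21%

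The difference falls from 0.83 to 0.42 points, and the placebo column is no longer empty.

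**The case against.** The strongest reply is that no effect has been shown. Planned and received groupings are identical unless someone took a wrong kit, and the documents report neither a case nor a rate. Assignment is central through the IWRS (Protocol 7.3), and the list in Protocol 9.2.8 is a generic set of error categories. The shares m and the size of 30 per sequence have no source in the documents. The factor 1−2m assumes crossover for a whole period, whereas one wrong pen is about a tenth of Treatment Period exposure. The safety outputs are counts, percentages and listings with no hypothesis test. The deviation counts and dosing listing give some visibility.

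All of that stands as a limit on size. It does not defend the rule. The deviation counts and dosing listing leave the events where they are, and the SAP does not say whether either would expose a kit-level discrepancy. Descriptive tables are still read as a comparison of treatments.

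A reader might infer that every participant changes kit at Visit 7, making errors especially likely there. The documents do not support that: half of the participants who had relamorelin continue on it (Protocol 5.2; SAP 6.5). A reader might also infer many dispensing visits, but the Schedule of Activities is not shown, so their number can only be guessed from pen life.

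**Conclusion.** The point holds conditionally. SAP 6.4 and 6.5 prescribe planned-treatment grouping for safety in populations defined by receipt, and nothing in either document corrects it. If a participant took a wrong kit, their adverse events and PCS laboratory values go under a treatment they were not taking.

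The effect is nil with no wrong-kit cases. For common events it is probably small: at most 2% relative attenuation at m = 1% and 6% at m = 3%, and far less if the error is a single pen in the Treatment Period. For rare events such as deaths, serious events or ketoacidosis, one case can change how a table reads. All these sizes rest on assumed wrong-kit shares, and the per-participant figures also require that the participant had the event.

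A reader might go further and conclude that the safety tables are wrong, or that a harm signal has been hidden. The documents do not support either reading, because they record no wrong-kit case. Nor does the SAP contradict the protocol, which is silent on arm assignment. The change is still worth making, because the rule is explicit, safety is the main content of the report, and the repair is cheap.

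**What to change.** In SAP 6.4, state that Safety Population analyses group participants by the treatment actually received in the Treatment Period. In SAP 6.5, state that RW safety uses the sequence actually received, while RW efficacy stays as randomised.

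Pre-state a rule for mixed exposure within a period. Assigning a participant to whichever treatment they took for most of the period is not enough: one wrong pen in about ten would leave the participant, and the event on that pen, in the planned arm. Two workable options are:
- count a participant with any relamorelin exposure in the period under relamorelin, which errs toward attributing events to the active drug; or
- attribute each event to the treatment being taken at its onset, with denominators defined to match.

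Add a listing of every participant whose planned and actual treatment differ, showing the treatment at the onset of each event. If there are none, one sentence in the report saying so closes the point.

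The cost is a few sentences in the SAP, one listing, and an actual-treatment variable derived from the dosing records (SAP 9), site dispensing records (Protocol 7.6) and IWRS assignments (Protocol 7.3). The documents do not say whether kit-level data are held centrally, so the derivation may need queries to sites. Safety group sizes may differ slightly from the efficacy groups and would need a footnote.

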6.5 Randomized Withdrawal Population

The Randomized Withdrawal (RW) Population will consist of all participants who are re-randomized or assigned to a treatment of the RW Period and receive ≥ 1 administration of study treatment during the RW Period. For the RW Period, there are 3 treatment sequences as follows:

1. Placebo - 10 μg (Placebo BID in the Treatment Period, followed by Relamorelin 10 μg BID in the RW Period)
2. 10 μg - 10 μg (Relamorelin 10 μg BID in the Treatment Period, followed by Relamorelin 10 μg BID in the RW Period)
3. 10 μg - Placebo (Relamorelin 10 μg BID in the Treatment Period, followed by placebo BID in the RW Period)

For the analyses based on RW Population, participants will be analyzed according to the treatments they are planned in the lead-in studies RLM-MD-01 and RLM-MD-02 and the RW period.

7 Participant Disposition

Screen failures (ie, participants who signed informed consent form, but did not enter the 40-week Treatment Period (ie, participants who were not dispensed study treatment at Visit 1 of this study)) and the associated reasons will be tabulated by treatment group and pooled across treatment group for the Screened Population. The number and percentage of participants who complete the double-blind Treatment Period and of participants who prematurely discontinue during the same period will be presented for each treatment group and pooled across treatment groups for the ITT Population. The reasons for premature discontinuation from the double-blind Treatment Period as recorded on the termination pages of the electronic case report forms will be summarized (number and percentage) by treatment group and pooled across treatment groups. All participants who prematurely discontinue during the double-blind Treatment Period will be listed by discontinuation reason.

Similar to the double-blind Treatment Period, the number and percentage of patients who are re-randomized into the RW Period, complete the RW Period, and prematurely discontinue from the RW Period will be presented overall and by treatment sequence for the RW Population. Reason for premature discontinuation from the RW Period as recorded on the trial completion forms of the eCRFs will be summarized (number and percentage) by treatment sequence.

The number and percentage with significant protocol deviations in the double-blind Treatment Period and in RW Period will be presented by treatment group and overall and by treatment sequence for the ITT Population and the RW Population, respectively.

8 Demographics and Other Baseline Characteristics

Demographic parameters (eg, age, age group, race, ethnicity, sex, geographic region), using the demographic and baseline data from lead-in studies RLM-MD-01 and RLM-MD-02, will be summarized in total and by treatment group for the Safety Population and RW Population.

Abnormalities in participants' medical and surgical histories will be coded using the *Medical Dictionary for Regulatory Activities*, version 23.1 or newer. A data listing for medical and surgical histories will be presented.

Prior medication is defined as any medication started before the date of the first dose of double-blind study treatment from the lead-in studies RLM-MD-01 and RLM-MD-02. *Concomitant medication* is defined as any medication taken on or after the date of the first dose of double-blind study treatment in this study.

The *WHO Drug Dictionary*, Version B2 March 2017 or newer, will be used to classify prior and concomitant medications by WHO Drug Anatomical/Therapeutic/Chemical (ATC) category and drug preferred name. A data listing for prior and concomitant medications will be presented.

9 **Extent of Exposure**

A listing of the investigational product dosing records will be provided for ITT population.

10 Efficacy Analyses

The efficacy analyses for the double-blind Treatment Period will be based on the mITT Population. For the RW Period, the efficacy analyses will be based on the RW Population. Since the study was early terminated, only descriptive analyses for the primary and secondary efficacy endpoints will be performed.

Most efficacy parameters will be derived from the DGSSD, a 7-item, patient-reported daily diary designed to assess the severity of 6 core signs and symptoms of DG—nausea, abdominal pain, postprandial fullness, bloating, vomiting, and early satiety—and the frequency of vomiting episodes. For purposes of the analyses, weekly values will be calculated from the daily e-diary data. For weeks with less than 4 days of available DGSSD data, weekly values will be set to missing. The Day 1 for the efficacy endpoints in the double-blind treatment period of this study is the Day 84 of lead-in studies RLM-MD-01/02. Day 1 for the efficacy endpoints in the RW period is the re-randomization date.

For all analyses, the baseline is the baseline value from the lead-in study RLM-MD-01 or RLM-MD-02, derived from the DGSSD, will be the average of the two weekly values from the two-week Run-in period of the lead-in studies.

